## **Current Clinical Risk Scores**

Clinical risk scores do not bridge the critical gap to enable clinicians to individualize long-term treatment with DAPT. For example, Yeh and colleagues developed a predictive score, the DAPT score, which is a tool designed to simultaneously predict ischemic and bleeding risk (Yeh 2016). Registry data from Sweden (2006 to 2014) that followed 41,101 patients demonstrated that the score had a discrimination of 0.54 for cardiovascular and cerebrovascular events, and

0.49 for fatal or major bleeding (Ueda 2018). Thus, the DAPT score supports individualization of therapy, however, the predictive accuracy is not sufficient to effectively guide therapy.

[name] et.al. applied the DAPT score to patients enrolled in a single center pilot study ([name] 2020). Patients with DAPT score  $\geq 2$  had a predicted event rate of 7.6% and an observed event (MI, stroke, death) rate of 10.1%. High platelet FcγRIIa expression was evident in 55% of patients with DAPT  $\geq 2$ . The combination of DAPT  $\geq 2$  plus high platelet FcγRIIa expression was associated with an event rate of 15.4% whereas the combination of DAPT  $\geq 2$  plus low platelet FcγRIIa expression was associated with an event rate of 3.7% ( $p < 0.05$ ). The broad distribution of platelet FcγRIIa expression in patients with both high and low clinical risk scores and these study results suggest that platelet FcγRIIa expression can be used to discriminate higher and lower risk among patients categorized as high risk by clinical risk tools.

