### 9 STATISTICAL CONSIDERATIONS

#### 9.1 STATISTICAL HYPOTHESES

Specifically, the study hypotheses are:

1. Platelet expression of FcγRIIa is associated with risk of MI, stroke, and death.
2. Incorporating platelet expression of FcγRIIa into existing risk scores improves identification of patients at high risk of MI, stroke, and death.
3. Platelet expression of FcγRIIa is not associated with risk of major bleeding.

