#### 9.4.3 ANALYSIS OF THE SECONDARY OBJECTIVES

First Secondary Objective: Negative predictive value, positive predictive value, sensitivity, and specificity will be calculated. Prediction will be performed using a Cox regression model with the following predictors: platelet expression of FcγRIIa, sex, age, MVD, CKD, DM, and prior MI. Evaluation of the model's error rates will be based on a leave-one-out cross-validation approach. Additional models will evaluate the performance of the predictive model using a continuous measure of FcγRIIa with the performance of predictive models using various binary measures of FcγRIIa.

Second Secondary Objective: The adjusted Cox proportional hazards model described for the primary objective analysis will be used to compare the bleeding risk as a function of FcγRIIa expression, both as a continuous and as a binary variable.

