5.6 Objectives and Endpoints

The primary objective of the study is to determine whether platelet expression of FcγRIIa is associated with risk of MI, stroke, and death.

Secondary objectives are:

- Develop a score that combines clinical characteristics plus platelet expression of FcγRIIa to determine the risk of MI, stroke, and death.
- Determine whether platelet expression of FcγRIIa is associated with risk of major bleeding.

The primary endpoint is the composite of death, MI, and stroke. A secondary endpoint is clinically significant bleeding according to BARC type 2-5.

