5.7 Statistical Methods

5.7.1 Analysis of the Primary Objective

The primary analysis of the primary endpoint will be a Cox proportional hazards model. The dependent variable is the number of days from enrolment to the occurrence of a primary endpoint, with censoring at the last day of complete follow-up; independent variables will be FcγRIIa (measured in thousands), age in years, history of diabetes mellitus, prior revascularization, multi-vessel coronary artery disease (MVD) defined as ≥2 vessels or left main with a stenosis ≥50%, chronic kidney disease (CKD) defined as estimated glomerular filtration rate (GFR) < 60 ml/min/1.73 m², prior MI, hypertension, tobacco use, heart failure or LVEF<30%, previous stroke or transient ischemic attack, and peripheral arterial disease. Interest is in the FcγRIIa parameter: point estimate (increase in risk per 1000-unit increase in FcγRIIa), confidence interval and p-value. FcγRIIa will be declared to be associated with cardiovascular risk if the 2-sided p-value from this model is < 0.05.

A set of exploratory/sensitivity and subgroup analyses based on the Cox model will also be conducted.

- Instead of censoring at the last day of complete follow-up, censor at the last day of vital status follow-up
- FcγRIIa as the only covariate in the model
- Separate analyses of each component of the primary endpoint: MI and stroke, both censored at the last day of complete follow-up, and death, censored at the last day of vital status follow-up
- Run the primary model in subgroups defined by age (in decades), sex, history of diabetes and prior revascularization (including all covariates except the subgroup variable in the model)
- Run the primary model with the use of DAPT (any use prior to a primary endpoint), and its interaction with FcγRIIa, as additional covariates

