5.7.2 Analysis of the Secondary Objective

First Secondary Objective: Negative predictive value, positive predictive value, sensitivity, and specificity will be calculated. Prediction will be performed using a Cox regression model with the following predictors: platelet expression of Fc γ RIIa, sex, age, and clinical risk factors associated with increased cardiovascular risk. Evaluation of the model's error rates will be based on a leave-one-out cross-validation approach. Additional models will evaluate the performance of the predictive model using a continuous measure of Fc γ RIIa with the performance of predictive models using various binary measures of Fc γ RIIa.

Second Secondary Objective: The adjusted Cox proportional hazards model described for the primary objective analysis will be used to compare the bleeding risk as a function of Fc γ RIIa expression. One

model will include FcγRIIa as a continuous variable, and another using the dichotomized version of FcγRIIa selected as the optimal version for risk stratification.

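### Hypothesis 2 says that adding FcγRIIa improves identification of high-risk patients, but no visible analysis compares prediction with and without the marker

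*SAP*

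**What the plan says.** Hypothesis 2, in protocol 2.2 and 9.1, is that incorporating FcγRIIa "into existing risk scores improves identification of patients at high risk of MI, stroke, and death". The matching secondary objective is worded more narrowly: "Develop a score that combines clinical characteristics plus platelet expression of FcγRIIa" (SAP 5.6).

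The planned prediction model is a Cox regression. Protocol 9.4.3 gives its predictors as "platelet expression of FcγRIIa, sex, age, MVD, CKD, DM, and prior MI". SAP 5.7.2 gives FcγRIIa, sex, age "and clinical risk factors associated with increased cardiovascular risk". Both documents use leave-one-out cross-validation for this model.

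The only comparison between prediction models is in SAP 5.7.2, with parallel text in protocol 9.4.3: "Additional models will evaluate the performance of the predictive model using a continuous measure of" FcγRIIa, against models using binary measures of it.

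Among the sensitivity analyses in SAP 5.7.1, the one reduced model has "FcγRIIa as the only covariate in the model". The ROC curves there are also for the marker by itself.

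**The concern.** To say that a marker improves identification is to make a comparison: how well patients are identified with it and how well without it. The incremental claim is also the protocol's rationale. Protocol 2.1 argues that the DAPT score discriminates too weakly (0.54 for ischemic events in a Swedish registry). It then concludes from pilot data that "platelet FcγRIIa expression can be used to discriminate higher and lower risk among patients categorized as high risk by clinical risk tools".

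If the plan is followed exactly, the study will report an adjusted hazard ratio and the accuracy of a score that contains FcγRIIa. It will not report how much of that accuracy the clinical factors would have given alone. Protocol 2.3 expects the results to support a later trial using the marker as a precision tool, and the gain over clinical factors is the figure such a trial would need.

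**Working it through.** **1. Planned analyses set against Hypothesis 2**

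- Primary Cox model (SAP 5.7.1): FcγRIIa plus 11 clinical covariates. It tests the FcγRIIa coefficient at two-sided 0.05, and the decision rule is about association, which is Hypothesis 1.
- Marker-only Cox model (SAP 5.7.1): this drops the clinical factors and keeps the marker, the reverse of what is needed.
- Incidence rates and ROC curves by threshold (SAP 5.7.1): marker only.
- Prediction model (protocol 9.4.3, SAP 5.7.2): always contains FcγRIIa.
- Continuous against binary FcγRIIa (same sections): both sides contain the marker.

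No analysis section computes an existing risk score, fits a clinical-only prediction model, or names a change in C-index or a reclassification measure.

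**2. The protocol's own figures**

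Protocol 2.1 reports, for pilot patients with a DAPT score of at least 2, that 55% had high FcγRIIa, with event rates of 15.4% (high) and 3.7% (low). These reproduce the stated overall rate: 0.55 × 15.4% + 0.45 × 3.7% = 10.1%. The pilot therefore looked at the marker within a level of a clinical score. The current plan has no counterpart.

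The event budget is no obstacle. At 10 events per predictor, 80/10 = 8 predictors. The protocol 9.4.3 model uses 7, and the same model without FcγRIIa uses 6.

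**3. Why the hazard ratio does not give the gain**

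Model: hazard = λ₀ · exp(β·Z + log(HR)·M), with Z a standardised clinical score and M high FcγRIIa. Gain = C-index of (Z, M) minus C-index of Z alone.

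From the documents: 55% high; 10% events per year; 12 months' enrollment and an 18-month minimum, hence 18–30 months of follow-up; HR 2 (the effect used for power) and HR 4 (the effect suggested by preliminary results).

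Assumed: β = 0.14 or 0.56, and a marker–score correlation of 0 or 0.3. Correlation is plausible because protocol 9.4.2 links higher FcγRIIa to age, diabetes and prior revascularization.

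Large-sample results (1,000,000 simulated subjects per row; gains taken before rounding):

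| HR | Correlation | Clinical C | C with marker | Gain |
|---|---|---|---|---|
| 2 | 0 | 0.540 | 0.601 | 0.061 |
| 2 | 0.3 | 0.562 | 0.608 | 0.047 |
| 2 | 0 | 0.651 | 0.676 | 0.024 |
| 2 | 0.3 | 0.668 | 0.691 | 0.023 |
| 4 | 0 | 0.539 | 0.665 | 0.126 |
| 4 | 0.3 | 0.577 | 0.670 | 0.093 |
| 4 | 0 | 0.647 | 0.723 | 0.076 |
| 4 | 0.3 | 0.680 | 0.739 | 0.058 |

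At trial size (1,000 simulated trials of 800 subjects), the two HR 2 rows with the stronger clinical score give mean gains of 0.026 (SD 0.014) and 0.022 (SD 0.012). The same HR of 2 thus goes with a gain anywhere from about 0.02 to 0.06, depending on the clinical model.

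**4. Precision of the missing comparison**

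The SD of the estimated gain across simulated scenarios was 0.008–0.014. So 1.96 × 0.008 = 0.016 and 1.96 × 0.014 = 0.027, or about ±0.02 to 0.03.

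**The case against.** The strongest reply is that added value is already tested. The primary model adjusts FcγRIIa for 11 clinical factors, and for nested models a zero coefficient means no added information. That stands, and it would be wrong to infer that the plan ignores independent value. What the test leaves out is the size of the gain in identification, and it involves no existing score.

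A second reply is that the stated objective is only to develop a score, and the plan does that. This also stands, but Hypothesis 2 remains listed under Statistical Hypotheses.

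Three stronger readings are tempting, and the documents do not support them:

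- *A significant hazard ratio will often come with a trivial gain.* In the trial-size simulations at HR 2, 34% (correlation 0) and 45% (correlation 0.3) of significant trials showed a gain below 0.02. A normal curve with the same means and SDs gives nearly the same shares: Φ((0.02 − 0.026)/0.014) = 0.33 and Φ((0.02 − 0.022)/0.012) = 0.43. These shares are mostly sampling scatter around a fixed true gain, and the 0.02 line has no source in the documents. At HR 4, or with a clinical C-index near 0.54, the expected gain is well above it.
- *The clinical predictors have been left open.* SAP 5.7.2 does not list them, but SAP 5.5 describes the characteristics meant for the secondary analysis and points to references that are not in the available text. Protocol 9.4.3 does list them.
- *The accuracy measures are invalid.* The SAP says "Negative predictive value, positive predictive value, sensitivity, and specificity will be calculated" without a predicted-risk cut-off or time horizon. If they are meant for the marker itself, as in the pilot, the 1,750 threshold in SAP 5.7.1 is the cut-off. This calls for clarification and is not a defect that carries the point.

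**Conclusion.** The concern holds for the comparator. In the visible text, no analysis measures prediction with FcγRIIa against prediction without it, so the plan as written cannot answer Hypothesis 2. This rests on reading the plan and needs no simulation. The reservation is that some SAP pages are not in the available text.

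The simulated gains only illustrate that the adjusted hazard ratio does not determine the improvement: about 0.02–0.03, 0.04–0.06 or 0.06–0.13 in C-index, depending on the effect and the clinical model. They rest on the assumed strength of the clinical score, the assumed correlation and a binary marker, and they do not predict what the study will find.

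The change should be made before outcomes are analysed. The primary analysis and its inference are unaffected.

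**What to change.** In SAP 5.7.2, add the same Cox prediction model without FcγRIIa: sex, age and the same clinical risk factors. Say which set is meant, either the protocol 9.4.3 list (MVD, CKD, DM, prior MI) or the set intended by SAP 5.5. Fit both models on the same subjects; SAP 5.9 already excludes anyone without a baseline FcγRIIa value. Report the cross-validated C-index with and without FcγRIIa, and the difference with a confidence interval.

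Describe the result as the gain over clinical risk factors unless an existing score, such as the DAPT score, can be computed from the collected data. The documents do not show whether it can. Changing the wording of Hypothesis 2 itself would be a protocol amendment needing IRB approval, whereas describing the result this way in the SAP would not change the protocol.

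As a clarification only, state the predicted-risk cut-off and time horizon for PPV, NPV, sensitivity and specificity.

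The cost is a few lines of SAP text and a little more analysis. The cross-validation is already planned and no new data are needed. The drawback is precision: an interval of about ±0.02 to 0.03 is as wide as the smaller gains above, so a modest improvement may not be distinguishable from none.

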## 4 STUDY DESIGN

### 4.1 OVERALL DESIGN

This is a prospective, observational multicenter non-interventional cohort study designed to integrate into the regular standard of care (Figure 5, Schematic Overview). Subjects who are admitted to the hospital with an MI will be screened. Screening will entail review of the medical

record for selected entry criteria. If the subject meets entry criteria, written informed consent will be obtained. Subjects will be enrolled into the study (called Day 1) before discharge from a hospitalization for a confirmed type 1 MI (STEMI or non-STEMI), referred to as the index event. Subjects will not have their care altered by participation in the study; subjects' medical regimens will be determined by their health care provider. Enrollment of subjects who are receiving anticoagulants for atrial fibrillation or venous thromboembolic disease will be limited to approximately 100 subjects.

[figure not shown]
After informed consent is obtained and the subject eligibility is confirmed, each subject will be assigned a unique identifier. Clinical characteristics and biochemical results will be associated with the unique identifier. The association between the subject's identity and the unique identifier will be kept in a secure file. Clinical characteristics will be recorded and blood (approximately 3 ml to 6 ml) will be obtained for analysis of platelet FcγRIIa expression. Blood can be taken up to 2 weeks post-study enrollment. The samples for platelet FcγRIIa expression will be assayed by a core laboratory to ensure standardization.

Subjects will be contacted by telephone every 6 months and asked a standardized set of questions to determine whether they have had a cardiovascular event (MI, stroke), bleeding event or have died. At each study visit, subjects will be queried about their medications with a specific focus on their anti-thrombotic regimen. Changes to their anti-thrombotic regimen will be documented in association with the time when changes were made. All subjects will be contacted at the end of the study for a final telephone visit. Medical records will be reviewed to confirm subject reported endpoints.

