### 6.1 MEDICATIONS

Anti-thrombotic therapy will be recorded in the case report form (CRF).

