#### 9.4.2 ANALYSIS OF THE PRIMARY OBJECTIVE

Cox proportional hazards models will be fit to compare the risk of the primary endpoint based on platelet expression of FcγRIIa as a continuous variable. Subjects will be followed until their earliest MI, stroke, or death. Patients who do not experience the composite endpoint will be censored at their last telephone follow-up. Time to the primary endpoint will be calculated as days from study enrollment. Models will be adjusted for potential confounders including sex and other subject demographics and medical history collected at baseline. In the pilot study, it was observed that older age, diabetes mellitus, and prior revascularization were associated with higher platelet FcγRIIa expression.

A set of sensitivity analyses will evaluate FcγRIIa as a binary endpoint, which each analysis using a different threshold for classifying FcγRIIa as high or low. In particular, these analyses will explore whether a binary or a continuous measure of FcγRIIa provides greater predictive value, and whether or not a threshold of  $\geq 11,000/\text{platelet}$  is optimal.

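### The bleeding model has no term for baseline anticoagulant use, although up to about 100 of 800 subjects may be anticoagulated; the resulting confounding is probably modest but avoidable.

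*SAP*

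**What the plan says.** SAP 5.7.2 defines the bleeding analysis by reference: "The adjusted Cox proportional hazards model described for the primary objective analysis will be used to compare the bleeding risk". It is run twice, once with continuous FcγRIIa and once with the dichotomized version chosen as best for risk stratification.

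The model is in SAP 5.7.1. Besides FcγRIIa it contains age, diabetes, prior revascularization, multi-vessel disease, chronic kidney disease, "prior MI, hypertension, tobacco use, heart failure or LVEF<30%, previous stroke or transient ischemic attack, and peripheral arterial disease". That makes 11 covariates and 12 terms in all. None is an antithrombotic drug, and neither atrial fibrillation nor venous thromboembolism is listed.

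The only drug term in any SAP model is in an exploratory run of the ischemic analysis: "Run the primary model with the use of DAPT (any use prior to a primary endpoint), and its interaction with" FcγRIIa. It is defined by use up to a primary endpoint, not by the Day 1 regimen. SAP 5.7.2 specifies no such run for bleeding.

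On adjustment, Protocol 9.4.2 says: "Models will be adjusted for potential confounders including sex and other subject demographics and medical history collected at baseline". Medication is not named. (Sex is named there but is absent from the SAP list, which is a separate matter.)

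On the population, Protocol 4.1 says: "Enrollment of subjects who are receiving anticoagulants for atrial fibrillation or venous thromboembolic disease will be limited to approximately 100 subjects". The Schedule of Activities (Protocol 1.3) places an antithrombotic medication review on Day 1 and at every telephone visit, and Protocol 6.1 has the therapy recorded in the CRF.

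**The concern.** The third hypothesis in Protocol 9.1 is that FcγRIIa is not associated with major bleeding. A conclusion of that kind can be spoiled in either direction. If anticoagulated subjects are more common among those with high FcγRIIa, an association can appear that is not due to the marker. If they are more common among those with low FcγRIIa, a real association can be masked.

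Baseline anticoagulation is an obvious candidate for such a confounder. Up to one subject in eight may be exposed, the exposure can be expected to raise bleeding, and the study already records it. The protocol itself accepts that antithrombotic intensity drives bleeding: Section 2.1 cites 2.5% against 1.6% moderate or severe bleeding with continued dual antiplatelet therapy. At stake is how far the bleeding HR can be read as belonging to the marker rather than to the treatment mix.

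**Working it through.** **Step 1. Number of bleeds under the plan's own inputs.** SAP 5.10 assumes 5% bleeding in the low group, HR 1.93, N = 800, two-sided α = 0.05, and states 95% power.
- High-group risk under proportional hazards: 1 − 0.95^1.93 = 9.43%.
- Events with equal groups: 400 × 0.05 + 400 × 0.0943 = 57.7. With 55% high, the share Protocol 2.3 reports for higher-risk pilot subjects: 59.5.
- Schoenfeld power with 57.7 events: Φ(√(57.7 × 0.25) × ln 1.93 − 1.96) = Φ(0.54) = 0.70.

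The stated 95% does not reproduce. Other two-sided methods and group splits give 66% to 72%, and about 121 events would be needed. If 5% were a yearly rate with about 2 years' mean follow-up, there would be 111 to 114 events and 93% to 94% power, but the text does not say per year. That discrepancy is separate from this point; only the event count is needed here.

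**Step 2. Precision of the bleeding HR.** The 95% CI factor is exp(1.96/√(events × 0.25)).
- 57.7 events: exp(0.516) = 1.68; the SE of log HR is 0.263.
- 40 events (5% of 800, no association): exp(0.620) = 1.86.
- 110.8 events (yearly reading): exp(0.372) = 1.45; SE 0.190.

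**Step 3. Size of the possible confounding.** For binary FcγRIIa, the bias factor is

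B = [1 + p_high(R − 1)] / [1 + p_low(R − 1)],

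where R is the bleeding HR for anticoagulation and p is the anticoagulated proportion in each FcγRIIa group. From the documents come the overall proportion, 100/800 = 12.5%, with the cap taken as filled, and the 55% high share. R and the imbalance are not in the documents; the ranges used, R = 1.5 to 3 and differences up to ±10 points, are assumptions.

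| High minus low | p_high / p_low | B at R = 1.5 | B at R = 2 | B at R = 3 |
|---|---|---|---|---|
| −10 points | 8.0% / 18.0% | 0.954 | 0.915 | 0.853 |
| −5 points | 10.25% / 15.25% | 0.977 | 0.957 | 0.923 |
| 0 | 12.5% / 12.5% | 1.00 | 1.00 | 1.00 |
| +5 points | 14.75% / 9.75% | 1.024 | 1.046 | 1.084 |
| +10 points | 17.0% / 7.0% | 1.048 | 1.093 | 1.175 |

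For example, R = 3 at +10 points gives (1 + 0.17 × 2)/(1 + 0.07 × 2) = 1.34/1.14 = 1.175. With 440 high and 360 low subjects, +10 points means about 75 against 25 anticoagulated.

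**Step 4. Bias against precision.** With 57.7 events, the extremes are ln 1.175/0.263 = 0.61 SE and ln 0.853/0.263 = −0.60 SE. At ±5 points and R = 3 they are about ±0.3 SE. On the yearly reading the upper extreme is 0.161/0.190 = 0.85 SE. At the extremes a true HR of 1.0 would be estimated at about 0.85 to 1.18, and a true 1.93 at about 1.65 to 2.27.

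**Step 5. Cost in model terms.** The model has 12 terms for about 58 bleeds: 57.7/12 = 4.8 events per term, against the guideline of 10 that SAP 5.10 cites. One more coefficient gives 57.7/13 = 4.4. A stratification factor adds no coefficient.

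**The case against.** Several counter-arguments carry weight.

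- **Drug and assay.** Protocol 2.3 reports that antiplatelet and anticoagulant agents do not alter platelet FcγRIIa. This rules out the drug changing the marker. It does not rule out confounding by indication, where a subject's characteristics influence both FcγRIIa and the chance of being anticoagulated.
- **Existing adjustment.** Age, chronic kidney disease, hypertension, heart failure and stroke/TIA are in the model. The baseline factors the protocol links to FcγRIIa (age, diabetes, prior revascularization) are there too. This removes an unknown part of the bias, so the Step 3 figures size it before that removal. What remains runs through atrial fibrillation and thromboembolism, which are not covariates.
- **Pilot balance.** The pilot found antiplatelet agents balanced by FcγRIIa level, but that covered clopidogrel and ticagrelor, not anticoagulants.
- **Reuse of the list.** It is deliberate and matches Protocol 9.4.3. Protocol 2.3 also notes that markers of thrombotic risk tend to mark bleeding risk.
- **Estimand.** The objective concerns a marker, and conditioning on treatment is partly a choice. This stands, and is a reason to show both results.

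Stronger readings are tempting. A reader might infer a spurious HR as high as 1.27, but that needs R = 3 with 5% against 20% anticoagulated (1.40/1.10), and nothing in the documents supports such an imbalance. A reader might also infer that the list was left behind when version 4.0 removed the anticoagulation exclusion. The documents do not show when the list was drawn up. Finally, a reader might require an antiplatelet term as well. All pilot patients took aspirin with clopidogrel or ticagrelor, so dual versus single therapy may hardly vary on Day 1.

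**Conclusion.** The concern holds as an avoidable gap of modest size. The bleeding model omits baseline anticoagulant use, its two named indications are also absent, and the information is collected on Day 1.

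Under the assumed ranges, the FcγRIIa bleeding HR could be off by a factor of about 0.85 to 1.18, or 0.92 to 1.08 at a 5-point imbalance. If use is balanced there is no bias. These figures assume that the cap is filled, that FcγRIIa is dichotomized with 55% high, and that the existing covariates remove nothing. They do not size the bias for the continuous FcγRIIa model. With about 58 bleeds, sampling error is larger than the bias throughout the range, so a shift of this kind would matter mainly when the result lies close to a decision boundary.

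The documents do not support the inference that the planned bleeding analysis is invalid or that a finding of no association would be overturned. The case for change is that the safeguard costs almost nothing and is more credible if fixed before the bleeding data are analysed.

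**What to change.** In SAP 5.7.2, stratify both bleeding Cox models (continuous and dichotomized FcγRIIa) by baseline anticoagulant use, yes or no, taken from the Day 1 medication review. Define yes to match the group the cap describes, so that short-term in-hospital use is not counted. Report the unstratified models alongside.

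Baseline antiplatelet regimen is optional, as a sensitivity analysis only, and only if it varies enough on Day 1 to be informative. It would add a coefficient to a model that already has fewer than 5 events per term.

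The cost is a sentence of SAP wording, one extra model line per analysis and a very small loss of precision. No new data, visits or coefficients are needed, and clinical care is untouched.
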